4.6.7.4. Hypoglycemia

Per the study protocol, investigators should use the following definitions and criteria when diagnosing and categorizing an episode considered to be related to hypoglycemia (the blood glucose values in this section refer to values determined by a laboratory or International Federation of Clinical Chemistry and Laboratory Medicine blood-equivalent glucose meters and strips) in accordance with the 2020 American Diabetes Association position statement on glycemic targets (ADA 2020) as below. Level 2 and Level 3 hypoglycemia events are considered as safety topics of special interest.

- **Level 1 Hypoglycemia (Level 1):**

Glucose less than 70 mg/dL (3.9 mmol/L) and glucose greater than or equal to 54 mg/dL (3.0 mmol/L)

- **Level 2 Hypoglycemia (Level 2):**

Glucose less than 54 mg/dL (3.0 mmol/L)

- **Severe Hypoglycemia (Level 3):**

Severe hypoglycemia (in adults): a severe event characterized by altered mental and/or physical status requiring assistance for treatment of hypoglycemia. For example, participants had altered mental status and could not assist in their own care or were semiconscious or unconscious, or experienced coma with or without seizures, and the assistance of another person was needed to actively administer carbohydrate, glucagon, or other resuscitative actions. Glucose measurements may not be available during such an event, but neurological recovery attributable to the restoration of glucose concentration to normal is considered sufficient evidence that the event was induced by a low glucose concentration.

- The determination of a hypoglycemic event as an episode of severe hypoglycemia, as defined above, is made by the investigator based on the medical need of the participant to have required assistance and is not predicated on the report of a participant simply having received assistance.
- If a hypoglycemic event meets the criteria of severe hypoglycemia, the investigator must record the event as serious on the AE CRF and report it to Lilly as an SAE.

- **Other hypoglycemia categories:**

Nocturnal hypoglycemia is a hypoglycemia event (including severe hypoglycemia) that occurs at night and presumably during sleep.

To avoid duplicate reporting, all consecutive hypoglycemic events occurring within a 1-hour period will be considered as a single hypoglycemic event.

Both the incidence (percent of patients experiencing 1 episode or more) and the rate (episodes/patient/year) of level 2 or level 3 hypoglycemia, and level 1 hypoglycemia will be reported by treatment group. For these analyses, only hypoglycemia events prior to permanent discontinuation of study drug will be included. A listing of all events of severe hypoglycemia may be provided, if deemed necessary. This listing will provide treatment allocation, clinical characteristics of the hypoglycemic event, and concomitant medications.

Summary of level 1 hypoglycemia will be provided for the data in SS and the data in SS excluding hypoglycemic events occurring after initiation of a new antihyperglycemic therapy.

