The most common treatment-emergent adverse events (TEAEs) were gastrointestinal (GI) events, including vomiting (with higher doses), abdominal distention, and nausea, which were dose dependent, mostly mild in severity, occurred within 4 days of dosing, and resolved within a week of onset. Dose-dependent increases in heart rate (HR) and decreases in systolic blood pressure (BP) were observed, which returned to near baseline by Day 29.

Across dose levels, the maximum observed drug concentration (C_{max}) occurred between ~1 and 3 days postdose, while the mean terminal half-life was ~5 to 7 days, thus supporting a QW dosing regimen.

Study J1I-MC-GZBB (GZBB) is a Phase 1, randomized, investigator- and participant-blind study that assessed the safety, tolerability, and PK/PD effects of multiple doses of LY3437943 when administered QW in participants with T2D. Trulicity[®] (dulaglutide) 1.5 mg was used as an active comparator. Participants in Cohorts 1 to 3 received fixed doses of LY3437943 (0.5, 1.5, and 3 mg QW) or placebo for 12 weeks. Participants in Cohorts 4 and 5 received placebo or LY3437943 titrated from a starting dose of 3 mg QW to maximum doses of 6 mg QW (Cohort 4) and 12 mg QW (Cohort 5) over the 12-week treatment period.

Based on preliminary data from this ongoing study, 72 participants received study treatment, and 43 completed the study to date. Gastrointestinal adverse events (AEs) (nausea, abdominal distention, and diarrhea) and decreased appetite were the most frequently reported events, mostly mild in severity and dose dependent. A dose dependent increase in HR was noted. The HR effects were consistent with those of the GLP-1 or GIP/GLP-1RA class, as was seen in Phase 1 clinical development. There were no reports of severe hypoglycemia or AEs related to the site of injection. Overall, data from early phase clinical trials support further development of LY3437943 in Phase 2 studies.

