8.3.2. Adverse Events of Special Interest

The following are adverse events of special interest and will be adjudicated by an independent clinical endpoint committee (CEC):

- pancreatitis
- major adverse cardiovascular events, and
- deaths.

The following are additional adverse events of special interest for this program that will not be adjudicated by an external committee:

- hypoglycemia (Level 2 and 3)
- thyroid malignancies and C-cell hyperplasia
- supraventricular arrhythmias and cardiac conductive disorders
- hypersensitivity events
- injection site reactions

- hepatobiliary disorders
- severe GI AEs
- antidrug antibodies
- acute renal events, and
- depression, suicidal ideation or behavior monitoring.

Sites should collect additional details and data regarding these safety topics, as instructed on the applicable eCRFs, and detailed below.

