Treatment effect of interest is thus defined as the difference in mean percent changes in body weight at Week 24 between QW LY3437943 and placebo.

Rationale for “efficacy estimand”: This Phase 2 study aims to study the efficacy of LY3437943 under the ideal condition that all participants adhere to the randomized treatment.

Estimand(s) for Secondary Objectives

The same estimand for the primary objective will be used for the following efficacy endpoints for the secondary objectives:

- difference between LY3437943 and placebo in percent change from baseline in body weight at Week 48
- percentage of participants with 5% or higher, 10% or higher, and 15% or higher body weight loss from baseline at Weeks 24 and 48
- change from baseline in body weight (kg) at Weeks 24 and 48
- change from baseline in BMI (kg/m²) at Weeks 24 and 48; and
- change from baseline in waist circumference (cm) at Weeks 24 and 48.

Unless specified otherwise, safety and tolerability assessments will be guided by an estimand comparing safety of LY3437943 doses with placebo for the whole study period (the treatment period plus safety follow-up period) irrespective of adherence to study intervention for all study population (including inadvertent enrollment).

Supplemental Estimand(s) for Primary Efficacy Endpoint

An alternative estimand, called “hybrid estimand”, is the mean treatment difference in percent change in body weight from baseline at Week 24 between LY3437943 and placebo in participants who meet the inclusion criteria with ICEs handled differently according to the reasons for the events:

- Category 1: The ICEs of permanent discontinuation of study drug due to reasons unlikely related to the efficacy/safety outcomes will be handled by the hypothetical strategy.
- Category 2: The ICEs of permanent discontinuation of study drug due to lack of efficacy before study treatment discontinuation will be handled by the hypothetical strategy
- Category 3: All other ICEs will be handled by the treatment policy strategy. With treatment policy strategy, the occurrences of “permanent discontinuation of study drug” is considered irrelevant in defining the treatment effect of interest. The value for the response variable is used regardless of whether or not the ICE occurs.

Population-level summary: mean percent change in body weight at Week 24.

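### The SAP gives the wider safety-set hypoglycemia summaries to Level 1 only, although Level 2 and Level 3 are the events of special interest

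*SAP*

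**What the plan says.** SAP 4.6.7.4 plans that the incidence and the rate "of level 2 or level 3 hypoglycemia, and level 1 hypoglycemia will be reported by treatment group". It then limits those analyses: "only hypoglycemia events prior to permanent discontinuation of study drug will be included". The section closes with a further output: "Summary of level 1 hypoglycemia will be provided for the data in SS and the data in SS excluding hypoglycemic events occurring after initiation"; the therapy in question is a new antihyperglycemic one. No matching sentence covers Level 2 or Level 3.

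The same section states that "Level 2 and Level 3 hypoglycemia events are considered as safety topics of special interest", and protocol 8.3.2 also lists Level 2 and 3, not Level 1, as adverse events of special interest.

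SAP 1.1, 4.1 and 4.6 set the default safety estimand as irrespective of adherence, analyzed on the SS. SAP 3 defines the SS as treatment-period plus follow-up data, regardless of adherence. Each statement of the default allows exceptions that are specified elsewhere.

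**The concern.** The category that the plan ranks lower gets the fuller analysis. For Level 1 a reader will see an on-drug count, a count over the whole study, and a count with later glucose-lowering therapy taken out. For Level 2/3 only the on-drug count is planned. The SAP gives no reason, and its version history says that version 3.0 was meant to make clear that safety parameters use the safety analysis set.

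Two things are at stake:

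- **Lost events.** Protocol 7.1 keeps participants in the study for all planned safety measures after they stop drug. Level 2 events from that time are collected but enter no planned hypoglycemia summary.
- **Attribution.** Protocol 6.5.2 permits sulfonylureas and basal insulin for incident type 2 diabetes, and protocol 8.3.2.1 names both as commonly associated with hypoglycemia. The SAP handles this confounder for Level 1 but not for the events of special interest.

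**Working it through.** There is no stated figure to reproduce; the question is which events reach which output.

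**Step 1: planned outputs by level.**

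| Output | Level 1 | Level 2 | Level 3 |
|---|---|---|---|
| Incidence and rate before permanent discontinuation (SAP 4.6.7.4) | Yes | Yes, combined with Level 3 | Yes, combined with Level 2 |
| Summary on SS (SAP 4.6.7.4) | Yes | No | No |
| Summary on SS without events after new antihyperglycemic therapy (SAP 4.6.7.4) | Yes | No | No |
| AE/SAE tables and narratives (SAP 4.6.2, 4.6.3) | Only if serious | Only if serious | Yes, always an SAE |
| Laboratory shift table and abnormal listing (SAP 4.6.6) | Visit glucose | Visit glucose | Visit glucose, if sampled |
| Severe-event listing with concomitant medications (SAP 4.6.7.4) | No | No | Optional |

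The on-drug restriction therefore applies to every level. The asymmetry lies in rows two and three.

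**Step 2: follow a non-serious Level 2 event after early discontinuation.** Protocol 8.3.2.1 sends it to the hypoglycemia eCRF and keeps it off the AE form. It is outside the on-drug incidence and rate, and the SS summaries do not cover its level. If it was found on a visit sample, it appears as a low glucose in the laboratory outputs; the shift table uses the performing laboratory's limits, not the 54 mg/dL cut-off. If it was found on a home meter, no planned table shows it.

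**Step 3: could such an event occur under exposure?** Protocol 2.2 reports for the single-dose study that "the mean terminal half-life was ~5 to 7 days". Fraction remaining = 0.5^(t / half-life):

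| Days | Half-life 5 days | Half-life 7 days |
|---|---|---|
| 7 | 0.5^1.4 = 38% | 0.5^1 = 50% |
| 14 | 0.5^2.8 = 14% | 0.5^2 = 25% |
| 28 | 0.5^5.6 = 2% | 0.5^4 = 6% |
| 35 | 0.5^7 = 1% | 0.5^5 = 3% |

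The first two weeks or so after the last dose carry material exposure; the later weeks carry little.

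**Step 4: the rate.** SAP 4.6.7.4 expresses it as episodes per patient per year but does not define the person-time. If on-drug events were divided by whole-study time, the rate would be too low in any arm with early discontinuation.

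**The case against.** The strongest case against is that the SAP breaks no rule of its own. The default safety estimand gives way wherever something else is specified, and SAP 4.6.7.4 does specify something else. An on-drug count is also a reasonable main analysis, because participants who stop early may be followed to Week 48, mostly unexposed. Both points stand, so this is not a breach of the estimand, and the on-drug count should stay.

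The other outputs also limit the loss, and this stands too. Level 3 events must be reported as SAEs, so they reach the AE/SAE overview on the SS. Each such participant gets a narrative with patient-level data, in which glucose-lowering therapy can be examined. Glucose is in the chemistry panel, which is scheduled through Visit 801. Home glucometers go only to participants with incident diabetes, or to others at the investigator's discretion.

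Three stronger readings are tempting, but the documents do not support them:

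- A reader might infer that Level 1 escapes the restriction, or that the section contradicts itself on Level 1. Neither follows. The restriction covers Level 1 incidence and rate, and a separate SS summary can stand beside them.
- A reader might infer that every participant loses the whole wash-out, since protocol Appendix 5 equates five half-lives with 30 days. That requires finishing treatment to count as permanent discontinuation. Protocol 7.1 and the intercurrent event in SAP 1.1 use the term for stopping early. On that reading completers lose nothing, and the excluded time in early stoppers has no fixed length.
- A reader might infer that the loss would change a comparison between arms. The documents give no event rate to support this. Diabetes and glucose-lowering drugs are excluded at entry, and metformin is named as the initial therapy for incident type 2 diabetes.

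None of this explains why the two wider summaries cover Level 1 and not the events of special interest.

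**Conclusion.** The point holds in a narrow form, as a minor improvement. The planned hypoglycemia summaries omit Level 2/3 events after permanent discontinuation. Allowing for the SAE and laboratory routes, the real gap is non-serious Level 2 events after early discontinuation, chiefly those not found on a visit sample. Separately, no planned summary distinguishes Level 2/3 events that follow newly started glucose-lowering therapy; for Level 3 the narratives help case by case.

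The effect cannot be quantified and may be small. For scale only, Protocol 9.2 assumes 20% dropout. With 300 randomized, each dose group and placebo has 300 × 2/10 = 60, of whom 60 × 0.20 = 12 would drop out. Using dropout as a stand-in for early drug discontinuation is an assumption: the two are not the same, and only a few of those participants, if any, would have a qualifying event.

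The conclusion assumes that permanent discontinuation means stopping early. If the sponsor means it to include the end of planned treatment, completers' follow-up would be excluded as well, and the SAP should say so.

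**What to change.** Change the last sentence of SAP 4.6.7.4 so that both summaries, on the SS and on the SS without events after a new antihyperglycemic therapy, also cover the incidence and rate of Level 2/3. Keep the existing on-drug analysis alongside. For each rate, define person-time to match its event window: time to permanent discontinuation for the on-drug rate, time to end of study participation for the SS rate, and time to the start of new therapy (where it occurs) for the third.

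If that sentence was meant to name Level 2/3 rather than Level 1, correct it at the same time.

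The cost is a few more table rows, using data already collected and summaries already planned for Level 1. The drawback is that the full-SS count includes some unexposed time, which is why the on-drug count should remain beside it.

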4.6.7.5. Immunogenicity

Treatment-emergent anti-drug antibodies are defined as those with a titer 2-fold (1 dilution) greater than the minimum required dilution if no ADAs were detected at baseline (treatment-induced ADA) or those with a 4-fold (2 dilutions) increase in titer compared to baseline if ADAs were detected at baseline (treatment-boosted ADA). A patient is evaluable for TE ADA if the patient has a nonmissing baseline ADA result, and at least 1 nonmissing postbaseline ADA result.

Listings of patients who are not TE ADA evaluable, patients with at least 1 test having detected LY3437943 ADAs, and patients having LY3437943 ADAs present or TEAE: hypersensitivity reactions or injection site reactions will be provided.

The frequency and percentage of patients with preexisting ADA, with TE ADA, with cross-reactive antibodies and with neutralizing antibodies will be tabulated by dose (if data warrant), where proportions are relative to the number of patients who are TE ADA evaluable. The frequency and percentage of patients with hypersensitivity and injection site reaction TEAEs by TE ADA status will be tabulated if data warrant.

4.6.7.6. Hypersensitivity Events

Hypersensitivity reactions and related information reported in electronic case report form (eCRF) will be listed and summarized by treatment.

Two main analyses are performed:

- **Potential Immediate Hypersensitivity:** Analysis of TEAEs occurring from the start of study drug administration up to 24 hours after the end of study drug administration. For events without the hypersensitivity eCRF, only date (no time) information is collected, the events occurred on the same date as the study drug injection date will be included.
- **Potential Non-Immediate Hypersensitivity:** Analysis of TEAEs occurring more than 24 hours after the end of study drug administration, but prior to subsequent study drug administration.

Summaries of all potential hypersensitivity reactions will be generated by PT with decreasing frequency by treatment. The AE database will be searched using predefined SMQs to identify events consistent with hypersensitivity events. Severe/serious hypersensitivity events identified by predefined SMQ search will be considered as AESIs.

4.6.7.7. Injection Site Reactions

Injection site reactions, incidence, and related information reported in eCRF will be summarized by treatment. Information to be summarized includes the timing of the reaction relative to study drug administration, and characteristics of the injection site reaction: erythema, induration, pain, pruritus, and edema.

Additionally, potential injection site reactions will be searched by predefined MedDRA HLTs of injection site reactions, administration site reactions, and infusion related reactions. Detailed searching criteria for injection site reaction events can be found in Section 7.6 (Appendix 6). The PT will be used for summary by treatment within each HLT category. Only the severe/serious injection site reactions will be considered as AESI.

4.6.7.8. Renal Safety

Laboratory measures related to renal safety will be analyzed as specified for laboratory measurements in Section 4.6.6.

Two shift tables examining renal function will be created. A min-to-min shift table of eGFR estimated by the CKD-EPI equation with unit mL/min/1.73 m², using categories (less than 30, greater than or equal to 30 to less than 45, greater than or equal to 45 to less than 60, greater than

or equal to 60 to less than 90, and greater than or equal to 90 mL/min/1.73 m²). A max-to-max shift table of UACR, using the categories UACR less than 30 mg/g, greater than or equal to 30 mg/g and less than or equal to 300 mg/g, UACR greater than 300 mg/g (respectively, these represent normal, microalbuminuria, and macroalbuminuria).

Mixed model repeated measure analyses for eGFR and UACR will be provided. Log transformation will be performed for UACR.

4.6.7.8.1. *Acute Renal Events*

Because severe GI events may lead to dehydration, which could cause a deterioration in renal function including acute renal failure, dehydration events will be analyzed. Acute renal events associated with chronic renal failure exacerbation will also be captured.

Acute renal events will be considered as AESI.

The counts and percentages of participants with acute renal events will be summarized by treatment by using the MedDRA PTs contained in any of the following SMQs:

- Acute renal failure: narrow terms in Acute renal failure SMQ (20000003), and
- Chronic kidney disease: narrow terms in Chronic kidney disease SMQ (20000213).

In addition, a listing of participants with treatment-emergent acute renal events may be provided, if deemed necessary.

4.6.7.8.2. *Dehydration*

Dehydration events will be captured in the narrow terms in Dehydration SMQ (20000232).

A listing of participants with treatment-emergent dehydration events will be provided.

4.6.7.9. *Thyroid Safety Monitoring*

4.6.7.9.1. *Calcitonin*

Observed calcitonin data (a thyroid-specific laboratory assessment) will be summarized by treatment and nominal visit.

The counts and percentages of participants with a maximum postbaseline calcitonin value in the following thresholds will be provided by treatment and baseline calcitonin value (20 ng/L or lower, higher than 20 ng/L to 35 ng/L or lower, higher than 35 ng/L). Postbaseline: 20 ng/L or lower, higher than 20 ng/L to 35 ng/L or lower, higher than 35 ng/L to 50 ng/L or lower, higher than 50 ng/L to 100 ng/L or lower, and higher than 100 ng/L.

4.6.7.9.2. *C-Cell Hyperplasia and Thyroid Malignancies*

Thyroid malignancies and C-cell hyperplasia will be considered as AESI. Treatment-emergent thyroid malignancies and C-cell hyperplasia will be identified using Malignancies SMQ (20000090), MedDRA HLT for Thyroid neoplasms and PT for Thyroid C-cell hyperplasia.

The counts and percentages of participants with treatment-emergent thyroid C-cell hyperplasia and malignancies will be summarized by treatment and PT ordered with decreasing frequency. In addition, a listing of participants with treatment-emergent thyroid C-cell hyperplasia and neoplasms may be provided if deemed necessary.

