	The C-SSRS, Self-Harm Supplement Form should be administered after assessment of adverse events. For this study, the C-SSRS is adapted for the assessment of the ideation and behavior categories only. The Intensity of Ideation and Lethality of Behavior sections are removed.																					
Columbia-Suicide Severity Rating Scale (C-SSRS) (Since Last Visit Version)			X	X	X	X	X	X	X	X	X	X	X	X	X	X	X	X	X	X	X	
Self-Harm Supplement Form	X		X	X	X	X	X	X	X	X	X	X	X	X	X	X	X	X	X	X	X	
Self-Harm Follow-up Form	X		X	X	X	X	X	X	X	X	X	X	X	X	X	X	X	X	X	X	X	
	Self-Harm Follow-up Form is only required if triggered by the Self-Harm Supplement Form, per instructions in the form.																					
Laboratory Tests and Sample Collections																						
Hematology	X			X			X	X			X			X			X		X		X	
HbA1c	X			X				X			X			X			X		X		X	
Urinalysis	X																					
Chemistry panel (includes creatinine for eGFR)	X			X			X	X			X			X			X		X		X	

	Study Period I Screening			Study Period II Treatment														99	ED	Study Period III Post- Treatment Safety Follow-Up		
	1	2	3	4	5	6	7	8	9	10	11	12	13	14	15	16	17			48	801	
Visit (see Notes below)	1	2	3	4	5	6	7	8	9	10	11	12	13	14	15	16	17	99	ED	801		
Week of Treatment	-6	-3	-1	0	1	4	8	12	16	20	24	28	32	36	40	44	48	48		4 Wks post end of TXP		
				Titration period																		
Allowable Interval Tolerance (days)	±7	±7	±7	-	±2	±3	±3	±3	±7	±7	±7	±7	±7	±7	±7	±7	±7	±7		±7		
Fasting Visit	X	X		X	X	X	X	X	X	X	X			X			X	X	X	X		
Telephone Visit												X	X		X	X						
calculation and glucose)	The CKD-EPI equation will be used by the central lab to estimate and report eGFR.																					
Lipid panel	X			X			X	X			X						X		X	X		
Longitudinal biomarkers				X			X	X			X						X		X			
	See Section 10.10 (Appendix 10) for list of biomarkers																					
Endpoint biomarkers				X							X						X		X			
	See Section 10.10 (Appendix 10) for list of biomarkers.																					
Serum pregnancy	X																					
	For women of childbearing potential only.																					
Urine pregnancy (local)				X				X			X			X			X		X			

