8.3.2.12. Acute Renal Events

Renal safety will be assessed based on repeated renal functional assessment as well as assessment of AEs suggestive of acute renal failure or worsening of preexisting chronic renal failure. Gastrointestinal AEs have been reported with LY3437943, including nausea, diarrhea, and vomiting. This is consistent with other GLP-1R agonists (Aroda and Ratner 2011). These events may lead to dehydration, which could cause a deterioration in renal function, including acute renal failure. Participants should be advised to notify investigators in case of severe nausea, frequent vomiting, or symptoms of dehydration.

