4.6.6. Clinical Laboratory Evaluation

All laboratory data will be reported in SI units. Selected laboratory measures will also be reported using CN units. Limits from the performing lab will be used to define low (L) and high (H). Descriptive summaries by treatment and by nominal visit will be provided for the baseline and postbaseline values as well as the change from baseline values.

Observed and change from baseline values for each visit may be displayed in plots for participants who have both a baseline and at least 1 postbaseline planned measurement. Baseline will be the last nonmissing observation prior to taking first study drug. Unplanned measurements will be excluded from plots.

A shift table will be provided including unplanned measurements. The shift table will include the number and percentage of participants within each baseline category (low, normal, high, or missing) versus each postbaseline category (low, normal, high, or missing) by treatment. The proportion of participants shifted will be compared between treatments using Fisher's exact test.

For qualitative laboratory analytes, the number and percentage of participants with normal and abnormal values will be summarized by treatment.

A listing of abnormal findings will be created for laboratory analyte measurements, including qualitative measures. The listing will include participant identification, treatment group, laboratory collection date, study day, analyte name, and analyte finding.

The MMRM model as described in Section 4.3.2 or ANHECOVA (if MMRM model is not applicable) as described in Section 4.3.3 will be used for the analysis during the treatment period for the continuous measurements for selected lab tests. The ANHECOVA, if used in this case, will use EAS with multiple imputation performed by applying only hypothetical strategy to ICE.

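### The only filtration analyses named in the SAP use creatinine eGFR, which muscle loss may bias upward by arm; the scheduled cystatin C gets no eGFR and no named renal analysis

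*SAP*

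**What the plan says.** **Basis of eGFR.** The protocol's Schedule of Activities (Section 1.3) has the row "Chemistry panel (includes creatinine for eGFR" and adds that "The CKD-EPI equation will be used by the central lab to estimate and report eGFR". Protocol Appendix 2 lists a single calculated eGFR (CKD-EPI). It lists cystatin C separately, among the biomarkers.

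**Renal analyses.** Protocol Section 8.3.2.12 says "Renal safety will be assessed based on repeated renal functional assessment", together with renal adverse events. SAP Section 4.6.7.8 names:

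- "A min-to-min shift table of eGFR estimated by the CKD-EPI equation" and a second shift table for the urine albumin/creatinine ratio (UACR);
- models: "Mixed model repeated measure analyses for eGFR and UACR will be provided";
- events: "The counts and percentages of participants with acute renal events will be summarized by treatment", plus a dehydration listing.

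**Route for other analytes.** The same section opens with "Laboratory measures related to renal safety will be analyzed as specified for laboratory measurements in Section 4.6.6". Section 4.6.6 then gives: "Descriptive summaries by treatment and by nominal visit will be provided for the baseline and postbaseline values as well as the change from baseline values". It adds a shift table against laboratory limits, and a model for a subset of tests that it does not list. The readable SAP text never names cystatin C, and neither document defines an eGFR from it.

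**The concern.** Creatinine comes from muscle. If treatment reduces muscle mass, creatinine production falls and creatinine eGFR rises with no change in filtration. That is general physiology; neither document discusses it.

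It matters here because the bias need not be equal across arms. Protocol Section 4.3 expects more weight loss with higher dose. The sample size section assumes -8% versus placebo at Week 24, and the SAP includes a responder threshold of 30% or more. The NAFLD addendum measures lean thigh muscle volume, but nothing links it to renal safety. An upward bias that grows with weight loss would offset a true decline most in the arms losing most weight, in a trial whose data support Phase 3 dose selection. The second filtration marker is already being drawn, but the plan does not turn it into a filtration estimate.

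**Working it through.** The documents state no figure for this point, so there is none to reproduce. The check has two parts.

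**1. Where the two markers are scheduled** (Schedule of Activities, read by column position)

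| Time point | Chemistry (creatinine) | Cystatin C |
|---|---|---|
| Visit 1 (screening) | yes | yes |
| Visit 4 (Week 0) | yes | no |
| Visit 7 (Week 8) | yes | no |
| Visit 8 (Week 12) | yes | no |
| Visit 11 (Week 24) | yes | yes |
| Visit 14 (Week 36) | yes | no |
| Visit 17 (Week 48) | yes | yes |
| Visit 99 | no | yes |
| Early discontinuation | yes | yes |
| Visit 801 (follow-up) | yes | yes |

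The markers coincide at 5 of the 9 chemistry time points. SAP Section 4.1 takes baseline as the last value before first dose. That is normally Visit 4 for creatinine but Visit 1 for cystatin C. A participant who completes has 6 scheduled post-baseline creatinine values (Weeks 8, 12, 24, 36, 48 and follow-up) but 3 of cystatin C. A minimum taken over 6 values tends to be lower than one taken over 3, so min-to-min tables are comparable only if restricted to matching visits.

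**2. Possible size of the masking** (illustration; no input is in the documents)

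Assumptions: at steady state, creatinine is proportional to production divided by GFR; eGFR is proportional to creatinine^-1.2; production falls 5% or 10%; true GFR falls from 90 to 81 (factor 0.90).

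- No change in production: creatinine × 1/0.90 = 1.111; eGFR = 90 × 1.111^-1.2 = 79.3.
- Production down 5%: creatinine × 0.95/0.90 = 1.056; eGFR = 90 × 1.056^-1.2 = 84.3.
- Production down 10%: creatinine × 0.90/0.90 = 1.000; eGFR = 90.0.

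The reported value is therefore about 84-90. At a 5% fall in production, the share of the signal lost is (84.3 - 79.3)/(90 - 79.3) = 5.0/10.7, or about 47%. At 10% all of it is lost. If true filtration did not change, the same assumptions would give a false rise to 90 × 0.95^-1.2 = 95.7 or 90 × 0.90^-1.2 = 102.1.

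The share lost hardly depends on the exponent. With -0.30, the upper end of the -0.24 to -0.30 range assumed for low creatinine values, the three readings are 87.2, 88.5 and 90.0. The share lost at 5% is then 1.3/2.8, again a little under half. The false rise is smaller there (1-3%), but so is the response to a true fall.

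**The case against.** A reader might infer that renal safety in this trial rests on creatinine eGFR. It does not. UACR has its own shift table and model, acute renal events are counted by standardised queries, and dehydration is listed. None of these is defined by creatinine eGFR. A reader might also infer that cystatin C is drawn alongside every creatinine sample and then ignored. Neither part is right: it matches 5 of 9 time points, and the pointer to Section 4.6.6 arguably brings it into the descriptive laboratory output.

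Other points on that side carry weight:

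- The fall in production, the exponent and the break in the equation are outside assumptions, and the documents do not say which CKD-EPI version applies.
- The shift table is less vulnerable than the model. In the illustration a reading of 84 still leaves the category of 90 and above, so the shift is recorded; it disappears only when production falls by the full 10%.
- Apart from early discontinuation visits, no cystatin C is scheduled on treatment before Week 24. The analysis cannot address acute events during escalation, and dehydration after gastrointestinal events is the mechanism the documents describe.
- Cystatin C has non-renal determinants, including adiposity and inflammation. Adiposity is what the drug is meant to change, so this estimate too may be biased by arm, possibly in the same direction.

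These limit the claim but do not remove it. UACR measures albuminuria rather than filtration, and event counts can miss a subclinical decline. The general summaries give no cystatin C eGFR, do not use the eGFR categories, and leave open whether cystatin C is modelled. Because the two markers have different non-renal determinants, a disagreement between them would be informative, although agreement would not prove that filtration is unchanged.

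**Conclusion.** The point holds in a limited form. The two filtration analyses that the SAP names both use creatinine eGFR. The scheduled cystatin C has no named renal analysis, and no eGFR is derived from it. Under the stated assumptions, roughly half to all of a 10% true decline could be masked in the reported mean, and more so in arms that lose more weight. That size is an illustration. The documents give no creatinine or muscle-loss figure, so they do not support saying that a renal decline is hidden at the higher doses, only that the planned filtration analyses could not readily separate it from a fall in creatinine production. No efficacy conclusion, alpha level or power figure is affected. This is an inexpensive improvement that should be made, not a flaw that undermines the trial.

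**What to change.** In SAP Section 4.6.7.8:

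1. State that the existing eGFR is creatinine-based.
2. Add a cystatin C eGFR with its equation stated and, if wanted, a combined creatinine-cystatin C eGFR.
3. For it, provide a by-visit summary, a shift table in the same eGFR categories, and modelled change from the Visit 1 baseline to Weeks 24 and 48.
4. Show it beside creatinine eGFR at matching visits. For that comparison, take creatinine from Visit 1 as well, and restrict both shift tables to visits where both markers are drawn.
5. State the limits: Weeks 8, 12 and 36 cannot be covered, acute events during escalation are not addressed, and cystatin C has its own non-renal determinants, so neither estimate is read alone.

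The cost is SAP wording, one further set of summaries with a shift table, and one model. It needs no new samples and no change to the sample size.
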